2.2. Pooling Algorithm for Analysis Centers

There are 2 parts in this study and each part will primarily be evaluated separately. For each part, data from different study sites (if applicable) will be pooled for analysis. In addition, the study data will be analyzed based on the pooled (ie, 14-day interval vaccination schedule) data from

Parts 1 and 2 of the study, matching the cohorts (ie, healthy and HIV-infected subjects) and regimen (ie, vaccine sequence and interval).

2.3. Analysis Sets

Full Analysis Set

The full analysis set includes all subjects who were randomized and received at least 1 dose of study vaccine (Ad26.ZEBOV, MVA-BN-Filo or placebo), regardless of the occurrence of protocol deviations.

Immunogenicity Analysis Set

The immunogenicity analysis set includes all randomized and vaccinated subjects, who have at least 1 post-vaccination (ie, after the date of vaccination) evaluable immunogenicity sample.

Per Protocol Analysis Set

The per protocol analysis set includes all randomized and vaccinated subjects, who received both the dose 1 and dose 2 vaccinations (administered within the protocol-defined visit window), have at least 1 post-vaccination (ie, after the date of vaccination) evaluable immunogenicity sample, and have no major protocol violations influencing the immune responses.

The primary immunogenicity analysis will be performed on the per protocol analysis set. The analysis on the immunogenicity analysis set will be included as sensitivity analysis only if more than 10% of the subjects are excluded from the per protocol analysis set. For subjects who received dose 1 (ie, only first vaccination) but not dose 2 while continuing their planned visit schedule, the immune response measurements after the planned (ie, upper limit of the analysis visit window that covers the target day for the second vaccination) but not administered dose 2 will not be included in graphs and tables showing descriptive statistics. These measurements will however be shown in listings, together with the indication that they are not used in the analysis.

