6.2. Criteria for Postponement of Vaccination

A subject will not be given the prime or boost vaccination if he/she experiences any of the following events at the scheduled time for vaccination:

- Acute illness at the time of vaccination (this does not include minor illnesses such as diarrhea or mild upper respiratory tract infection)

Note: If a subject is acutely ill with malaria at the time of either prime or boost vaccination, at least 3 days must elapse from the conclusion of a standard, recommended course of therapy for malaria before vaccination.

- Fever (body temperature $\geq 38.0^{\circ}\text{C}$) at the time of vaccination

Subjects experiencing any of the events described above may be vaccinated up to 10 days beyond the window allowed for the scheduled vaccination, or be withdrawn from that vaccination at the discretion of the investigator and after consultation with the sponsor (see Section 10.2).

Note: In case the boost vaccination is postponed, the timing of the post-boost visits will be planned relative to the actual vaccination day (see Section 9.1.1).

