2.1. Analysis Visit Windows and Periods

Because subjects do not always adhere to the protocol visit schedule, the following rules will be applied to assign actual visits (immunogenicity and safety [ie, including only HIV viral load and CD4+ cell counts in HIV-infected subjects]) to analysis visits. The analysis visit windows and target days for each visit are displayed in [Table 2](#). The reference day will be defined as:

- Day of first (dose 1) vaccination if the actual visit occurs prior to the second (dose 2) vaccination.
- Day of second vaccination (dose 2) if the actual visit occurs after the second vaccination.

Only the analysis time points and assays that are in scope for final statistical analysis are to be considered when assigning assessments to analysis visit windows. If a subject has 2 or more assessments within the same interval (analysis visit window), the one closest to the target day will be used for generating tables with descriptive statistics and graphical displays presenting data per time point. If 2 assessments are equidistance from the target day within the same interval, the latest assessment will be used. All assignments will be made in chronological order.

Because the analysis of adverse events (AEs), vital signs and laboratory abnormalities (except HIV viral load and CD4+ cell counts in HIV-infected subjects) will be presented per period (and not per time point), these will be assigned to the analysis period and/or phase based on [Table 3](#).

For HIV viral loads and CD4+ cell counts in HIV-infected subjects, the electronic case report form (eCRF) visit schedules will be used for the post baseline assessments. If only unscheduled visits are present for a time point, then the one closest to the scheduled visit will be used. If distances of multiple assessments to the scheduled visit are equal, the measurement with the latest date will be used.

Table 2: Analysis Visit Windows

Time Interval (Label on Output)	Time Interval PP ^a (Day)	Time Interval IG ^b (Day)	Target Time Point (Day)
Prior to dose 2 vaccination			
Day 1 (Baseline)	≤ 1	≤ 1	1
Day 15 (14 days Post-dose 1)	[12; 18]	[2; 21]	15
Day 29 (28 days Post-dose 1)	[26; 32]	≥ 22	29
After dose 2 vaccination			
Day 36 (21 days Post-dose 2)	[19; 25]	[2; 32]	22
Day 50 (21 days Post-dose 2)			
Day 57 (42 days Post-dose 2)	[40; 46]	[33; 112]	43
Day 71 (42 days Post-dose 2)			
Day 195 (180 days Post-dose 2)	[166; 196]	[113; 273]	181
Day 209 (180 days Post-dose 2)			

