Day 380 (365 days Post-dose 2)	[336; 396]	≥ 274	366
Day 394 (365 days Post-dose 2)			

^a The analysis based on the per protocol (PP) analysis set will be restricted to data points that fall within this window (ie, protocol-defined window).

^b The analysis based on the immunogenicity analysis set will be restricted to data points that fall within this window.

Note 1: The analysis windows and target days are based on the relative day (ie, with respect to reference day [day of dose 1 or dose 2 administration]).

Note 2: Day of dose 2 is also considered as Day 1 with respect to the second vaccination (ie, for calculating target days that fall after the second vaccination).

Note 3: Day 36, Day 57, Day 195 and Day 380 apply only to the 14-day interval vaccination schedule. While Day 50, Day 71, Day 209 and Day 394 apply only to the 28-day interval vaccination schedule.

Table 3: Analysis Periods

Phase	Period	Interval	
		From	To
Screening		00:00 on the date of signing the informed consent form	One minute prior to dose 1 administration on Day 1
Regimen*	Post-dose 1	Date and time of dose 1 administration	Minimum of: 
 a) 23:59 on the date of last contact (for early study discontinuation) b) 23:59 on the date of relative Day 29 Post-dose 1 c) 23:59 on planned visit day of dose 2 administration (in case dose 2 is not administered) d) one minute prior to dose 2 administration [□] e) 23:59 on the date of database cut-off (in case of interim analysis)
Post-dose 1 FU		One minute after the end of the Post-dose 1 period	Minimum of: 
 a) 23:59 on the date of last contact (for early study discontinuation or completion) b) one minute prior to dose 2 administration c) 23:59 on the date of database cut-off (in case of interim analysis)
Regimen*	Post-dose 2	Date and time of dose 2 administration	Minimum of: 
 a) 23:59 on the date of last contact (for early study discontinuation or completion) b) 23:59 on the date of relative Day 29 Post-dose 2 c) 23:59 on the date of database cut-off (in case of interim analysis) 
Note: subjects who do not receive dose 2 will not have a Post-dose 2 period.

Post-dose 2 FU		One minute after the end of the Post-dose 2 period	Minimum of: 
 a) 23:59 on the date of database cut-off (in case of interim analysis) b) 23:59 on the date of last contact (for early study discontinuation or completion)

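### In the 28-day schedule, the SAP rule that drops samples after a missed dose 2 has no cut-off, because the immunogenicity-set Day 29 window has no upper limit

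*SAP*

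**What the plan says.** SAP 2.3 covers subjects who had dose 1, missed dose 2 and kept attending. Measurements after the planned "but not administered dose 2 will not be included in graphs and tables showing descriptive statistics"; they go to listings. The planned time is defined as the "upper limit of the analysis visit window that covers the target day for the second vaccination".

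The two pre-dose 2 rows of SAP Table 2 give, in order, the per-protocol window, the immunogenicity-set window and the target day:

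- "Day 15 (14 days Post-dose 1) [12; 18] [2; 21] 15"
- "Day 29 (28 days Post-dose 1) [26; 32] ≥ 22 29"

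Footnote b assigns the second window to the immunogenicity set: "The analysis based on the immunogenicity analysis set will be restricted to data points that fall within this window". Note 3 says which post-dose 2 labels belong to which schedule but does not mention Day 15 or Day 29. Under SAP 2.1, when several assessments fall in one window, the one nearest the target is used for per-time-point tables and graphs.

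The per-protocol set is limited to subjects "who received both the dose 1 and dose 2 vaccinations (administered within the protocol-defined visit window"). It carries the primary immunogenicity analysis. The immunogenicity set is a sensitivity analysis, run only if more than 10% of subjects are excluded from the per-protocol set (SAP 2.3).

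Protocol Table 2 gives the boost visit a window of ±3 days. Under Protocol 6.2, a subject who is acutely ill or febrile "may be vaccinated up to 10 days beyond the window allowed for the scheduled vaccination". Under Protocol 10.2, subjects taken off study vaccine normally stay in immunogenicity follow-up.

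**The concern.** A rule that depends on the upper limit of a window cannot act where the window has none. The rule is meant to stop a one-dose response, drawn months after the boost should have been given, from appearing among summary statistics for the regimen. In the 28-day schedule it gives the programmer no day to apply.

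The immunogenicity-set analysis exists to bring back subjects with a missed or late boost, so the windows need to work for them. The same two rows also serve both schedules, so a late boost in the 14-day schedule can move a sample into a row that describes a visit the schedule does not contain.

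**Working it through.** **1. Reproduce Table 2.** The per-protocol windows are the target day plus or minus the protocol visit window: 15±3 = [12; 18], 29±3 = [26; 32], 22±3 = [19; 25], 43±3 = [40; 46], 181±15 = [166; 196], 366±30 = [336; 396]. All match. The immunogenicity-set boundaries are midpoints between neighbouring targets: (15+29)/2 = 22, (22+43)/2 = 32.5, (43+181)/2 = 112, (181+366)/2 = 273.5. All match. The last row of each block has no later neighbour and is left open. Before dose 2, that row is Day 29, so the missing limit looks like a by-product of the midpoint method.

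**2. Which column governs the rule.** The per-protocol column has a limit (Day 32), but a subject without dose 2 is never in the per-protocol set. The rule can therefore matter only in the immunogenicity set, and footnote b ties that set to its own column.

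**3. Apply the rule to a subject who never gets dose 2**, counting days from dose 1:

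| Schedule | Cut-off | Scheduled draws kept | Draws dropped |
|---|---|---|---|
| 14-day | Day 21 | 15 | 36, 57, 195, 380 |
| 28-day | none | 29, 50, 71, 209, 394 | none |
| 28-day, if Day 32 were used | Day 32 | 29 | 50, 71, 209, 394 |

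**4. Apply the nearest-to-target rule in the 28-day schedule.** All five draws fall in the Day 29 window, and one is tabulated:

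- Day 29 draw present: Day 29 is used, which is correct.
- Day 29 draw missing: Day 50 is used (21 days off target). If that is also missing, Day 71 (42 days off), then Day 209 (180), then Day 394 (365).

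**5. Late boosts.** The latest boost under the protocol's allowance is Day 15+3+10 = 28 in the 14-day schedule and Day 29+3+10 = 42 in the 28-day schedule. A 28-day subject boosted on Days 33-42 has a pre-dose 2 sample in the Day 29 row, which is correct. A 14-day subject boosted on Days 22-28 has a pre-dose 2 sample outside [2; 21], which falls in the Day 29 row. If Day 29 is instead read as not applying to that schedule, the sample has no window. Either way it leaves the Day 15 row.

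**6. Other cut-offs.** SAP Table 3 ends the post-dose 1 period at the planned dose 2 visit when dose 2 is not given, but those periods serve adverse events, vital signs and laboratory abnormalities. No other cut-off for immunogenicity samples after a missed dose 2 was found.

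**The case against.** The strongest reply is that the nearest-to-target rule does most of the work. Immunogenicity blood is scheduled at the boost visit before vaccination, so a subject refused the boost that day will normally have a Day 29 sample. That sample is tabulated and the later ones are not. This stands. A reader might infer from the missing limit that all later samples of unboosted 28-day subjects enter the summaries. They do not: the exposure needs no dose 2, no sample near Day 29 and later attendance, all in one subject.

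A reader might also infer that the pre-dose 2 row is wrong for missed and late boosts generally. The documents do not support this. Late 28-day boosts are labelled correctly, as are missed 28-day boosts with a Day 29 draw, and the rule works for missed 14-day boosts. Nor do postponed 14-day boosts lose their pre-dose 2 anchor. SAP section 2 defines the immunogenicity reference value as the assessment on the date of dose 2, whatever Table 2 row it falls in, so fold increases from that value are unaffected. Only the day-labelled row is.

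Finally, SAP 2.3 does not say which Table 2 column it means, and footnote a calls the per-protocol column the protocol-defined window. Using its Day 32 limit would make the rule work. That reading is possible, but it borrows a window assigned to an analysis set that these subjects cannot enter. At the least, the SAP should say which is meant.

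**Conclusion.** The point holds as a narrow gap. In the immunogenicity set, the missed-dose 2 exclusion has a cut-off of Day 21 in the 14-day schedule and none in the 28-day schedule. Its visible effect is that an unboosted 28-day subject without a sample near Day 29 can have a sample from Day 50 to Day 394 shown as Day 29. A second, separate effect is that a pre-dose 2 sample from a 14-day boost on Days 22-28 leaves the Day 15 row.

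Neither effect touches the primary per-protocol analysis. Both arise only if the sensitivity analysis is triggered. The denominator for the 10% is not stated: more than 10% means at least 58 of the planned 575 subjects, or at least 41 of 400 if taken within Part 2, Group 1. The documents give no count of missed or postponed boosts, so the number of affected subjects cannot be stated; few are expected.

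The conclusion rests on two assumptions: that the immunogenicity-set column governs the rule, and that the visits of a never-boosted subject count as prior to dose 2, with dose 1 as the reference day. The SAP states neither outright, but both are the natural reading.

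**What to change.** In SAP Table 2, make the immunogenicity-set pre-dose 2 windows finite and specific to the schedule, using the protocol's own allowance of ±3 plus 10 days:

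- 14-day schedule: Day 15 row only, [2; 28].
- 28-day schedule: Day 29 row only, [2; 42].

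Extend Note 3 to assign Day 15 and Day 29 to their schedules, and state in SAP 2.3 that the exclusion after a missed dose 2 uses these upper limits.

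The limits do not reach the next scheduled immunogenicity draw, whose earliest day is 36−3 = 33 in the 14-day schedule and 50−3 = 47 in the 28-day schedule. The lower bound of 2 also stops an early 28-day sample, such as one at withdrawal, from taking a Day 15 label.

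The cost is two table cells, one note and one sentence. No new data are needed, and nothing changes in the primary analysis.

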2.4. Definition of Subgroups

There are 2 parts (Part 1: USA, Part 2: Africa) in the study with each part having the healthy and HIV-infected cohort of subjects aged 18-70 years. The subgroups that will be used to summarize the data are shown in [Table 4](#). Primarily, the analysis of subject information, safety and immunogenicity analyses will be performed by part and cohort. Within each combination of part, cohort and vaccination (dose 1 and dose 2) interval, subject information, safety and immunogenicity data will be presented for active vaccines (ie, vaccine sequence and interval) versus placebo.

Secondly, Part 2 data (ie, ELISA [units/mL] and VNA [IC₅₀ titers]) will be presented by age stratum and on the pooled cohorts (ie, healthy and HIV-infected).

In addition, data from Parts 1 and 2 will be pooled (matching on cohort and vaccination schedule).

For each combination of cohort and vaccine sequence, the pooled data (subject information, ELISA [units/mL], VNA [IC₅₀ titers] and safety) will be presented for active vaccine versus placebo. The pooled immunogenicity data (ELISA [units/mL] and VNA [IC₅₀ titers]) will also be presented by age stratum (aged 18-50 years and aged 51-70 years) for active vaccine versus placebo. Furthermore, these data will be presented on the pooled cohorts (healthy and HIV-infected).

Table 4: Study Part, Cohort, Dose 1-Dose 2 Interval and Age Group Combinations and Parameters

Study Part	Dose 1-Dose 2 Interval	Cohort	Age Group	Analysis Parameters	
Part 1	14-day interval	Healthy	18-70 years	
 - Subject information - ELISA (units/mL) - VNA (IC₅₀ titers) 	
		HIV-infected			
Part 2	14-day interval	Healthy	18-70 years	
 - ELISpot - ICS - Ad26 VNA (Part 2 only) - Safety 	
		HIV-infected			
		Healthy	18-50 years		
 - ELISA (units/mL) - VNA (IC₅₀ titers)
			51-70 years		
		HIV-infected	18-50 years		
			51-70 years		
	Pooled Healthy and HIV-infected	18-70 years			
	Part 2	28-day interval	Healthy	18-70 years	
 - Subject information - ELISA (units/mL) - VNA (IC₅₀ titers) - ELISpot - ICS - Ad26 VNA (Part 2 only) - Safety
			HIV-infected		
			Healthy	18-50 years	
			51-70 years		
HIV-infected			18-50 years		
			51-70 years		
Pooled Healthy and HIV-infected	18-70 years				
Pooled Parts 1 and 2	14-day interval	Healthy	18-70 years	
 - Subject information - ELISA (units/mL) - VNA (IC₅₀ titers) - ELISpot - ICS - Ad26 VNA (Part 2 only) - Safety 	
		HIV-infected			
		Healthy	18-50 years		
 - ELISA (units/mL) - VNA (IC₅₀ titers)
			51-70 years		
		HIV-infected	18-50 years		
			51-70 years		
Pooled Healthy and HIV-infected	18-70 years				

Note: There is currently no assay for the VNA (IC₅₀ titers) of HIV-infected subjects.

3. CHANGES TO THE PLANNED ANALYSIS

- Even in the absence of baseline immunogenicity samples, the post-baseline samples are of interest. Therefore, the immunogenicity analysis set is redefined to include subjects without baseline immunogenicity samples, provided that at least 1 post-vaccination (ie, after the date of vaccination) evaluable immunogenicity sample is available for the subjects.
- Because different levels of Post-dose 2 immune responses are expected for different vaccination schedules, the per protocol analysis set is redefined to exclude subjects whose second vaccination falls outside the protocol-defined window. Similar to the immunogenicity analysis set, the per protocol analysis set is also refined to include subjects without baseline immunogenicity samples
- Because of the lack of the necessary data to assess non-adherence, the planned additionally analysis restricted to HIV-infected subjects who adhere to antiretroviral therapy (ART) if more than 10% of the HIV-infected subjects exhibit non-adherence to ART will not be performed.

4. INTERIM ANALYSIS AND DATA MONITORING COMMITTEE REVIEW

An interim analysis was conducted when all subjects in Part 1 had completed the 21-day post second vaccination visit or discontinued earlier. The purpose of this interim analysis was to evaluate the effect of vaccination on the HIV viral load of HIV-infected subjects from a safety perspective. The independent statistical support group (SSG) performed this interim analysis and sent a blinded data package to the protocol safety review team for review. The SSG also prepared an unblinded data package for the independent data monitoring committee (IDMC) review and recommendations. The details of that interim analysis were provided in a separate IDMC charter³ and the associated IDMC SAP⁴. The current SAP is applicable to the final analysis (ie, when all subjects in Parts 1 and 2 have completed the last study-related visit or discontinued earlier).

Ad hoc IDMC reviews could be requested by the sponsor for any single event or combination of multiple events which were considered to jeopardize the safety of the subjects. For all cases, the data package and analysis results that would have contained any piece of unblinding information would have been kept in a strictly confidential place, with access for IDMC and SSG members only until unblinding of the study by the sponsor.

5. SUBJECT INFORMATION

Subject information will be analyzed based on the full analysis set. In general, the analysis will be presented (see [Table 4](#)) by part, cohort and pooled (ie, Parts 1 and 2 data of the MVA-BN-Filo followed by Ad26.ZEBOV vaccination schedule).

5.1. Disposition Information

The number and percentage of subjects randomized, vaccinated and entered in each analysis period will be tabulated. Subject assignment to vaccine regimen will be provided in a data listing (including the assigned regimen and the actual regimen received).

Furthermore, the number and percentage of subjects in the full analysis set who completed and those who discontinued together with the reason(s) for discontinuation will be tabulated and listed. This will be done for completion/discontinuation from second vaccination and from the trial.

5.2. Protocol Deviations

Subjects with protocol deviations will be identified prior to the database lock. The major protocol deviations will be summarized by deviation category. A listing of the major protocol deviations will also be generated. The major protocol deviations that have the potential to influence immune responses will be flagged in the listing.

5.3. Demographics and Baseline Characteristics

The following demographic characteristics will be summarized.

- Sex (Female/Male)
- Age (years)
- Age group (18-50 years versus 51-70 years)
- Race
- Ethnicity
- Height (cm)
- Weight (kg)
- Body mass index (BMI, kg/m²), calculated from baseline height and weight
- HIV type (HIV serotype 1, HIV serotype 2), only for HIV-infected subjects

5.4. Prior and Concomitant Medications

The analysis of pre-study and concomitant therapies will be based on the World Health Organization (WHO) drug coded terms as provided in the clinical database. If the coded term for a concomitant medication is missing, then the reported term will be used and flagged in the table. The concomitant therapies will be tabulated per period. Additionally, a listing of all pre-study and concomitant therapies will be provided. There will be special attention to analgesics/antipyretics (such as acetaminophen, non-steroidal anti-inflammatory drugs [NSAIDs] and aspirin) administered during the first 8 days (including the day of the vaccination) following each vaccination. Special attention will also be given to HIV-related concomitant therapies.

Based on their start and stop dates, concomitant therapies will be reported in each analysis period during which they were applied. For missing or partial start/stop dates the following allocation rules will be applied:

- In case of partial start or stop dates, the concomitant therapy records will be allocated to analysis periods using the available partial information, without imputations. If, for example, only month and year are available, these will be compared to the month and the year of the analysis periods, and the concomitant therapy record will be allocated to the period(s) where these date parts match.
- In case of a completely missing start date, the concomitant therapy will be considered as having started before the trial.
- In case of a completely missing end date, the concomitant therapy will be considered as ongoing at the end of the trial.

Remark: In addition to the date information, time information is considered to allocate concomitant therapies to periods and/or phases, if available.

